#### 9.2.2.2.2. Pharmacokinetics

- Correlation of PK exposure with efficacy/safety
- Population-based PK parameters

## 9.2.3. Exploratory Endpoints

### 9.2.3.1. Efficacy

- QOL as measured by EQ-5D-5L, and the memory and concentration items from the PRO-CTCAE library
- PFS2: PFS on next line therapy based on local assessments
- Subgroup analysis for efficacy and other endpoints may be explored as data becomes available

### 9.2.3.2. Biomarkers and Pharmacodynamics

- Determine the potential innate and acquired resistance mechanisms to DCC-2618 in GIST.
- Assess KIT/PDGFR mutations and mutant allele frequency at baseline and the treatment effect of DCC-2618 on KIT/PDGFR mutant allele frequency
- Evaluate the association of anti-tumor activity/safety of DCC-2618 with the following:
  - baseline KIT/PDFGRA mutation status

- expression of KIT protein in tumor
- expression or polymorphic variation in drug metabolic and/or drug transporter genes

### 9.2.3.3. Healthcare Utilization

- Changes over time in healthcare utilization

## 9.3. Populations for Analysis

The following populations will be used in the analysis:

- All Enrolled
- KIT Exon 11 Intent to Treat (Ex11 ITT)
- All Patients Intent to Treat (AP ITT)
- Safety
- PK
- KIT Exon 11 Per Protocol (Ex11 PP)
- All Patients Per Protocol (AP PP)

The all Enrolled Population is defined as all patients who signed the informed consent and met inclusion/exclusion criteria.

The KIT Exon 11 ITT (Ex11 ITT) Population is defined as all patients who are designated as having a mutation in KIT Exon 11 at the time of randomization. Patients in this population will be analyzed according to the treatment they were scheduled to receive.

The AP ITT Population is defined as all patients who are randomized. Patients in this population will be analyzed according to the treatment they were scheduled to receive.

The Safety Population is defined as all patients who are randomized and receive at least one dose of study drug. Safety population will be used for all safety analysis and treatment assignment will be based on the actual initial study treatment received.

The PK Population will include all randomized subjects who received at least 1 dose of DCC-2618 and had at least 1 non-missing PK concentration in plasma reported for DCC-2618 or DP-5439.

The KIT Exon 11 Per Protocol (Ex11 PP) Population is defined as the patients in the Ex11 ITT population with at least one post baseline tumor assessment who met all inclusion criteria, did not violate any exclusion criteria, and did not have any significant protocol violations/deviations considered to impact study integrity. The efficacy analysis on the Ex11 PP population is supportive and treatment group will be based on actual treatment received. Protocol violators resulting in exclusion from the PP population will be identified and documented prior to database lock.

Note: if a patient has a KIT exon 11 mutation, along with mutation(s) 1) in KIT exon 9 and/or PDGFRA, the patient will be randomized as having a KIT exon 11 mutation, unless the mutation allele frequency (MAF) data is available then the mutation with the higher MAF will be used to categorize the patient for the purposes of randomization; 2) in KIT other exon, the patient will be randomized as having a KIT exon 11 mutation.

The All Patients Per Protocol (AP PP) population is defined as all patients in AP ITT population with at least one post baseline tumor assessment who met all inclusion criteria, did not violate any exclusion criteria, and did not have any significant protocol violations/deviations considered to impact study integrity. The efficacy analysis on the AP PP population is supportive and treatment group will be based on actual treatment received. Protocol violators resulting in exclusion from the PP population will be identified and documented prior to database lock.

#### 9.4. Procedures for Handling Missing, Unused, and Spurious Data

Algorithms for imputing partial or missing dates are shown in [Table 16](#). AE end dates are imputed to facilitate calculation of AE duration.

**Table 16: Partial or Missing Date Algorithms**

Variable	Missing Day	Missing Day, Month	Missing Day, Month, Year
Date of Last Therapy/Date of Initial Diagnosis	Assign 1	Assign January 1 if prior to date of informed consent, otherwise use date of informed consent	Missing (do not impute)
Adverse Event/Start Date	Assign first day of month unless it is the month of first dose of study medication. Otherwise, assign date of first dose of study medication or AE end date (if not missing) whichever is earlier.	Assign January 1 unless the year is year of first dose of study medication. Otherwise, assign date of first dose of study medication or AE end date (if not missing) whichever is earlier.	Assign date first dose of study medication.
Adverse Event End Date	Assign the last day of the month or end of study date, whichever is earlier.	Assign December 31 or end of study date, whichever is earlier.	If ongoing, end date is missing. Otherwise, assign end of study date.

#### 9.5. Interim Analyses

No interim analyses are planned for the study.

#### 9.6. Adjustment for Multiple Comparisons

To control familywise type-I error at 0.05 level, the hypothesis tests for treatment difference will be performed according to the hierarchical testing sequence below:

1. PFS in Ex11 ITT (two-sided 0.05 level)
2. PFS in AP ITT (two-sided 0.05 level)
3. ORR in Ex 11 ITT (two-sided 0.05 level)
4. ORR in AP ITT (two-sided 0.05 level)
5. OS in Ex11 ITT (two-sided 0.05 level)
6. OS in AP ITT (two-sided 0.05 level)

The testing starts from PFS in Ex11 ITT and each subsequent endpoint will only be tested if all the testing preceding to it have been statistically significant. If the testing for any endpoint fails to meet statistical significance, the testing and p-value for all the subsequent endpoints will be nominal and statistical significance won't be claimed for all the subsequent endpoints.

## **9.7. Blinding**

This is an open-label study.

## **9.8. Statistical Methods**

### **9.8.1. General Methods**

Data collected in this study will be documented using summary tables and patient data listings. Continuous variables will be summarized using descriptive statistics (number of patients, mean, median, standard deviation, minimum, and maximum). Categorical variables will be summarized using frequencies and proportions. Time-to-event data will be summarized via Kaplan-Meier (KM) methodology using the 25th, 50th (median), and 75th percentiles with associated 2-sided 95% confidence intervals.

Unless specified otherwise, baseline measurements must be the most recent value prior to receiving the first dose of study medication. If an assessment is not available, then the last assessment prior to that visit would be used.

Medical history, AEs, and concurrent procedures will be coded using Medical Dictionary for Regulatory Activities (MedDRA). Prior and concomitant medications will be coded using the World Health Organization Drug Dictionary.

Unless specified, the ITT population is used for efficacy analysis and the safety population is used for the safety analysis. The primary and secondary efficacy endpoints will be analyzed for both the Ex 1 1 ITT and the AP ITT populations.

### **9.8.2. Disposition of Patients**

Patient disposition will be summarized overall for all patients who entered the study (i.e. signed the informed consent for the study and met inclusion/exclusion criteria). The number of patients in each population (enrolled, safety, PK, ITT, PP if applicable) and patients were removed from a population will be displayed. The number and proportion of patients who complete the study, as well as those who discontinue the study will be summarized along with the reason for discontinuation.

### **9.8.3. Demographic and Baseline Characteristics**

Demographic and baseline characteristics (including risk assessment for recurrence at study entry) will be summarized by for the Safety, ITT, and PP populations (35).

Medical history will be summarized overall for the Safety population.

### **9.8.4. Extent of Exposure**

The total number of patients who received study medication will be summarized by n and percentage. In addition, the number of cycles received will be displayed using continuous descriptive statistics. These analyses will be performed for the Safety population.

## 9.8.5. Efficacy Analysis

### 9.8.5.1. Primary Endpoint: Progression-Free Survival Analysis

The primary endpoint of PFS is defined as the interval between the date of randomization and the earliest documented evidence of disease progression based on the independent radiologic review, or death due to any cause. Patients who undergo surgical resection of target or non-target lesions, who have received other anticancer treatments for GIST, or patients who do not have a documented date of progression or death due to any cause will be censored at the date of the last assessment.

Analysis for PFS in AP ITT will be stratified by the randomization stratification factors (mutation status [KIT exon 9 vs. KIT exon 11 vs. KIT/PDGFRA WT vs. other KIT {absence of exon 9 or 11}/PDGFRA] and intolerance to imatinib [yes vs. no]). Analysis for PFS in Ex11 ITT will be stratified by intolerance to imatinib [yes vs. no]. The p-value will be from a 2-sided stratified Log-rank test at 0.05 significance level for evaluation of treatment difference. Point estimate of hazard ratio will be obtained from a Cox regression model with treatment and the randomization stratification factors as fixed factors and the associated 95% CI will be obtained using the Wald method. Median progression free survival time (mPFS) with 95% confidence interval will also be presented by treatment using KM methodology.

NOTE:

Rules of defining PFS events and censoring PFS will be elaborated in the statistical analysis plan (SAP). Sensitivity analysis for PFS will be specified in the SAP.

Analysis will be using the ITT population as the primary analysis and PP as supportive. Progression free survival will have sensitivity analyses performed which will be further detailed in the SAP.

### 9.8.5.2. Secondary Efficacy Endpoints

#### 9.8.5.2.1. Objective Response Rate Analysis

ORR is defined as the proportion of patients with a confirmed CR or PR based on the independent radiologic review. This analysis will be performed in the ITT population as the primary analysis and the PP population as supportive analysis. To be assigned a status of a CR or PR, changes in tumor measurements must be confirmed by repeat assessments that must be performed at least 4 weeks after the criteria for response are first met. Patients with unknown or missing response will be treated as non-responders, that is, they will be included in the denominator when calculating the proportion.

Analysis for ORR in AP ITT population will be stratified by the randomization stratification factors (mutation status [KIT exon 9 vs. KIT exon 11 vs. KIT/PDGFRA WT vs. other KIT {absence of exon 9 or 11}/PDGFRA] and intolerance to imatinib [yes vs. no]). Analysis for ORR in Ex11 ITT population will be stratified by intolerance to imatinib [yes vs. no]. For each population, the p-value will be based on a Cochran Mantel-Haenszel chi-square test for the association between treatment and ORR at 0.05 significance level; stratified Newcombe 95% confidence limits will be calculated for the difference in ORR between the treatment arms.

#### 9.8.5.2.2. Overall Survival

OS is defined as the interval between the date of randomization and date of death from any cause. Patients who are still alive or who are lost to follow-up will be censored at the date of last contact. OS will be analyzed using similar model as PFS and will be analyzed based on both Ex11 ITT and AP ITT separately.

#### 9.8.5.2.3. EORTC QLQ-C30

The EORTC QLQ C30 will be summarized by scales per the manual and treatments compared by role and physical function for both Ex11 ITT and AP ITT separately.

#### 9.8.5.2.4. DLQI

The total score for the DLQI will be calculated by summing the score of each question for both Ex11 ITT and AP ITT separately, per the scoring manual (see <http://sites.cardiff.ac.uk/dermatology/quality-of-life/dermatology-quality-of-life-index-dlqi/dlqi-instructions-for-use-and-scoring/>). Higher scores are associated with a lower the quality of life. The total score will be summarized using descriptive statistics, including proportions who are moderately impacted (a total score of six to ten points) and severely impacted (a score of eleven or more). In addition to the total score, continuous descriptive statistics will also be displayed by section as follows:

Section	Questions Included
Symptoms and Feelings	1,2
Daily Activities	3,4
Leisure	5,6
Work and School	7
Personal Relationships	8,9
Treatment	10

#### 9.8.5.2.5. GP5 Question from FACT-G

FACT-G: Functional Assessment of Cancer Therapy - General - is a validated and widely used questionnaire that can be used with cancer patients of any tumor type. It includes a question referred to as GP5 which asks, "I am bothered by side effects of treatment". The answer is provided by the patient who selects one of the following five choices: Not at all, A little bit, Some-what, Quite a bit, or Very much.

Effect sizes for the difference in mean GP5 scores between groups can be estimated as the mean difference divided by the pooled standard deviation. FACT-G will be summarized for both Ex 11 ITT and AP ITT separately.

#### 9.8.5.2.6. Time to Tumor Progression

The secondary endpoint of TTP is defined as the interval between the date of randomization and the earliest documented evidence of disease progression based on the independent radiologic review. Patients who undergo surgical resection of target or non-target lesions, who have received other anticancer treatments for GIST, who do not have a documented date of progression or death due to any cause, or who die prior to tumor progression will be censored at

the date of the last assessment. TTP will be analyzed using similar model as PFS for both Ex 11 ITT and AP ITT separately.

#### 9.8.5.2.7. *Disease Control Rate Analysis*

DCR will be calculated and summarized with n and percentage at 6, 9, and 12 months. Disease control will be defined as having a response (complete or partial) or SD. Fisher's Exact test will be used to investigate statistical differences between treatment groups for both Ex 11 ITT and AP ITT separately.

#### 9.8.5.2.8. *Progression-free Survival based on Investigator Assessment*

PFS is defined as the interval between the date of randomization and the earliest documented evidence of disease progression based on Investigator assessment, or death due to any cause. Differences between treatment groups will be evaluated using the same methodology as for the primary endpoint for both Ex 11 ITT and AP ITT separately.

#### 9.8.5.2.9. *Efficacy Based on Choi Criteria Based on Independent Radiologic Review*

The primary PFS, ORR, TTP, and DCR analyses will be repeated using the Choi criteria in place of mRECIST for both Ex 11 ITT and AP ITT separately.

### 9.8.5.3. **Exploratory Endpoints**

#### 9.8.5.3.1. *Memory and Concentration Items from PRO-CTCAE Library*

The Memory and Concentration Items from the PRO-CTCAE Library will be summarized with n and percentage for each question.

#### 9.8.5.3.2. *EQ-5D-5L*

The EQ-5D-5L will be summarized overall by n and percentage for each level of each dimension. The Cochran–Mantel–Haenszel test will be used to test differences between DCC-2618 and sunitinib. The EQ-VAS will be summarized using continuous descriptive statistics.

#### 9.8.5.3.3. *Efficacy*

- Progression free survival on the next line of therapy (PFS2) will analyze time from the start of next therapy
- to the progression or death on the next line of therapy using the same methods used for the primary analysis of PFS.
- Subgroup analysis may be done as data becomes available.

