1. INTRODUCTION

This Statistical Analysis Plan (SAP) describes the detailed methodology for summary and statistical analyses of data from clinical protocol DCC-2618-03-002 (INTRIGUE) based on Amendment 6 of the study protocol, dated 23 October 2020. This document may modify the plans outlined in the protocol and supersedes the previous versions of the SAP and the statistical sections of the protocol.

Populations for analysis, statistical methods, data handling rules, and formats for data presentation are described within this document. The statistical analyses and summary tabulations described in this SAP will provide the basis for the results sections of the Clinical Study Report (CSR) for this trial. Analysis plan of population pharmacokinetics (PK) and exposure-response analysis, pharmacodynamics data, and quality-of-life (QOL) data collected for exploratory objectives will be separately documented.

Any changes to the data analysis methods after the SAP is finalized will be described in the CSR.

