2.1.4. Exploratory Objectives

- To assess QOL during treatment as measured by:
 - Memory and concentration items from the PRO-CTCAE library
 - EQ-5D-5L
- To assess PFS on next line therapy (PFS2) based on local assessments
- To evaluate potential biomarkers in blood or tumor tissue which might predict response to ripretinib
 - To understand potential resistance mechanisms to ripretinib in GIST
 - To characterize KIT and PDGFRA mutations at baseline and ripretinib-driven longitudinal mutant allele frequency changes in plasma.
- To assess healthcare utilization

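### PFS2 is timed from the start of next therapy but compared between arms with the primary PFS methods, so the comparison is not randomised and leaves out the study-treatment period

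*Protocol*

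**What the plan says.** Protocol 9.8.5.3.3 gives the clock: "PFS2) will analyze time from the start of next therapy". The next bullet, which continues the sentence, gives the event and the method: "to the progression or death on the next line of therapy using the same methods used for the primary analysis of PFS". Protocol 9.2.3.1 labels the endpoint "PFS2: PFS on next line therapy based on local assessments" and classes it as exploratory.

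The borrowed methods are in Protocol 9.8.5.1. There the clock starts at randomisation: "The primary endpoint of PFS is defined as the interval between the date of randomization and the earliest documented evidence of disease progression". The test is between arms: "The p-value will be from a 2-sided stratified Log-rank test at 0.05 significance level for evaluation of treatment difference". A Cox hazard ratio with a Wald interval accompanies it. Protocol 9.8.1 makes ITT the default efficacy population.

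SAP Section 1 says that the SAP "supersedes the previous versions of the SAP and the statistical sections of the protocol". On PFS2, however, the SAP contains only the objective in 2.1.4: "To assess PFS on next line therapy (PFS2) based on local assessments". SAP Section 8 has no PFS2 definition, population, censoring rule or test. The analyses that SAP Section 1 sends to separate documents are population PK and exposure-response, pharmacodynamics, and exploratory quality of life; PFS2 is not among them.

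**The concern.** Starting a next therapy happens after randomisation. Not every patient reaches it, and the assigned drug influences who reaches it, when, and in what disease state. A test that starts there compares two groups selected after randomisation. A difference could come from that selection, from different next-line drugs in the two arms, or from a real carry-over effect, and the test cannot separate these.

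The rule also removes the interval in which the plan expects the arms to differ. A drug that delayed first progression and had no influence on what followed would show a PFS2 hazard ratio near 1. A reader who takes PFS2 as a measure of whether the study-treatment gain is kept through the next line would be misled.

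**Working it through.** The documents give no event count, power or effect size for PFS2, so there is no stated figure to reproduce. The check has two parts.

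**1. What the rule implies, from the text alone**

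- *Who enters.* A patient needs a next-line start date. A patient who died first, is still on study drug at the cutoff, or had no further therapy has none. The ITT default in Protocol 9.8.1 cannot be applied to an analysis in which some randomised patients have no time zero.
- *What is counted.* Time from randomisation to next therapy contributes nothing. Deaths on the next line count as events; deaths before it do not appear.
- *Whether the borrowed method fits.* SAP 8.1.1 censors primary PFS at the last evaluable progression-free assessment before new anticancer therapy, and Protocol 9.8.5.1 also censors patients who received other anticancer treatment. PFS2 starts at that therapy, so the rule cannot apply as written. The SAP 8.1.1 rule on consecutive missed assessments presumes scheduled imaging, whereas Protocol 6.10.2 collects next-line progression by calls every 3 months (±1 month).

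**2. Illustration of size**

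*From Protocol 9.1:* 213 patients per arm, 21-month accrual, first-PFS medians 9 and 6 months, so HR = 6/9 = 0.667. As a check that these are the plan's working inputs, 262 events at this HR give power Φ(½·√262·|ln 0.667| − 1.96) = Φ(1.32) = 0.907, against the stated 90%.

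*Assumed, not in the documents:* 10% of first PFS events are deaths; 80% of the other patients start a next line; next-line median 5 months in both arms; data cutoff at month 29 or 60; log-normal patient frailty, SD 0 to 1, shared by both periods. In the from-randomisation version, patients without a next line are given the same further time to event.

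With complete follow-up, the expected number entering is 426 × 0.90 × 0.80 = 307. With no frailty and the same next-line distribution in both arms, the next-line HR is 1 whatever the first-treatment effect.

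Results of 1,000 simulated trials per row, unstratified log-rank:

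| Frailty SD | Cutoff (months) | Entering, DCC-2618 + sunitinib | HR from next-line start | Rejection | HR from randomisation, all 426 |
|---|---|---|---|---|---|
| 0 | 29 | 112 + 130 | 1.000 | 4.3% | 0.712 |
| 0 | 60 | 150 + 153 | 0.996 | 4.7% | 0.704 |
| 0.5 | 29 | 111 + 126 | 1.033 | 6.3% | 0.755 |
| 0.5 | 60 | 146 + 151 | 1.016 | 5.5% | 0.768 |
| 1.0 | 29 | 106 + 120 | 1.057 | 6.3% | 0.799 |
| 1.0 | 60 | 137 + 144 | 1.052 | 6.9% | 0.828 |

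In every row fewer patients enter from the arm with longer PFS, most clearly at the early cutoff. That is selection by treatment. Changing to gamma frailty with variance 0.25 to 1.0 takes the number entering down to about 190 (variance 1.0, month 29). It takes the next-line HR up to about 1.08 and the from-randomisation HR up to about 0.89. Rejection under the written rule mostly stays between 4% and 8%, with 10% the highest value in any set of runs.

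**The case against.** **The SAP supersedes the rule.** SAP Section 1 displaces the protocol's statistical sections and SAP Section 8 plans no PFS2 test, so one can read the plan as containing no between-arm PFS2 comparison at all. This does not settle the matter. The SAP keeps the objective and neither replaces the rule nor defers it elsewhere. Either Protocol 9.8.5.3.3 governs or a stated objective has no analysis; the same SAP wording cures both.

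**The definition matches the name.** The documents consistently describe PFS on the next line, and time from next-line start measures that. No passage says that PFS2 is meant to show whether the first-treatment gain persists. This stands as a defence of the quantity as a description. It does not defend comparing the arms on it with methods built for a randomised comparison.

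**The stakes are low.** This stands in full. PFS2 is exploratory and absent from the hierarchy in Protocol 9.6 and SAP 8.5.

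**Stronger readings that the documents do not support.** A reader might infer that the trial's type I error is at risk; no alpha is spent on PFS2, and the simulated inflation is small and appears only under assumed frailty. A reader might infer that all deaths are ignored; deaths on the next line are events. A reader might take the gap between an HR near 1 and one of 0.70 to 0.89 as the size of a bias. The two analyses answer different questions, and the second carries forward the assumed 9 versus 6 month benefit by construction.

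**Conclusion.** The point holds, at low severity. As written, PFS2 is a between-arm test restricted to patients who started a next line, with the randomised treatment period left out and a borrowed censoring rule that cannot operate. These consequences follow from the text and need no simulation.

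The sizes are illustrative: about 190 to 300 of 426 patients entering, and an HR of about 1.00 to 1.08 against about 0.70 to 0.89 from randomisation. They rest on the protocol's medians and on assumed values for next-line uptake, next-line duration, deaths before the next line, cutoff and frailty. The practical risk is misreading: a real first-treatment benefit could appear as no PFS2 effect, or a slightly adverse one. No confirmatory conclusion is affected.

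**What to change.** Add a PFS2 section to the SAP:

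- **Definition:** time from randomisation to progression on next-line therapy by local assessment, or death from any cause, whichever comes first.
- **Populations:** Ex11 ITT and AP ITT, with the stratification used for primary PFS.
- **Censoring:** a rule specific to PFS2. Patients alive without next-line progression are censored at the last date their progression status was known, not simply at the last phone contact. The start of the first subsequent therapy does not censor.
- **Next-line description:** report time from next-line start by arm, with the number who started a next line and the therapies given, and no test.

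The cost is SAP wording. Protocol 6.10.2 already collects the next line, its start date and its progression date, and follows all patients until death or withdrawal of consent, so no new data item appears necessary. The remaining weakness is that progression dates gathered at 3-monthly calls are coarser than scheduled imaging; the section should say so.
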